Rationale for Study	To improve the length and quality-of-life outcomes for people with non-small cell lung cancer (NSCLC) by enlisting and engaging patients in the dissemination of the NCCN guidelines. This is a two-year software development and implementation project to develop and field-test a decision aid based on the NCCN patient guidelines for NSCLC. The study goal is to improve the treatment decision-support process and experience for NSCLC patients in an academic medical center.
Primary Objective	
The primary study outcomes will emerge from measurement of changes in overall practice patterns after implementation of the decision aid. Pre- and post-intervention data will be used to determine the level of difference before and after implementation of the decision aid into the thoracic oncology clinics. Six specific practice patterns will be queried in a binary (yes/no) manner:
 
 1. All stages: smoking cessation discussion reinforced with a specific follow up plan and/or medication/patch/psychotherapy or counseling; 2. stage IB, IIA, IIB receiving surgery: adjuvant chemotherapy given after surgery; 3. stage III receiving surgery: pathologic staging of mediastinal nodal disease prior to initiation of therapies; 4. stage III not receiving surgery: pathologic staging of mediastinal nodal disease prior to initiation of therapies 5. stage III patients not receiving surgery: if concurrent chemotherapy and radiation are given upfront; 6. stage IV: molecular testing for EGFR and ALK mutations prior to initiation of systemic therapy.

Secondary Objectives	
Secondary objectives are to:
 
 1. Determine agreement between patient and physician post-consultation reports of treatments discussed and recommended, prognosis, and expected tolerance. 2. Determine correlations between overall and lung cancer-specific quality of life and decision-support preferences. 3. Determine correlations between overall and lung cancer-specific quality of life and decisional conflict. 4. Determine correlations between overall and lung cancer-specific quality of life and satisfaction with decision. 5. Determine correlations between decision-support preferences and decisional conflict and satisfaction with decision. 6. Determine correlations between decisional conflict and satisfaction with decision.
Study Design	
This study involves the evaluation of the decision support tool Patients with Power, previously used with breast cancer patients, in the non-small cell lung cancer patient population.
 
 1. Characterize physician and patient populations and treatment decisions in the UCSF thoracic oncology practices. 2. Establish the acceptability, feasibility, and effectiveness of a novel decision aid for decisions made about treatment for NSCLC. 3. Conduct an evaluation of changes in NCCN-guided practice patterns before and after implementation of the decision aid, with respect to 6 clinical scenarios: 
 • All patients: if smoking cessation intervention is provided at initial visit; • Stage IB-IIB patients receiving surgery: if adjuvant chemotherapy is given after surgery; • Stage III patients receiving surgery: if pathologic staging of mediastinal nodal disease is done prior to initiation of therapies; • Stage III patients not receiving surgery: if pathologic staging of mediastinal nodal disease is done prior to initiation of therapies; • Stage III patients not receiving surgery: if concurrent chemoradiation is given upfront; • Stage IV patients: if molecular testing is done prior to initiation of systemic therapy. 4. Collect data to facilitate the design of future larger-scale evaluations, including assessments of physician-patient agreement and patients' levels of decisional conflict and satisfaction with decisions made as well as potential correlations to patient-reported quality of life.

Number of patients	250
Duration of Intervention	The patients will have access to the decision support tool indefinitely (lifetime) but collection of all study metrics will end at 12 months after the period of their first 2 initial consultations for NSCLC.
Duration of Follow up	Questionnaires will be completed at the time of initial consultation, with no planned follow up; PwP website-based metrics will be followed in aggregate for a maximum of 1 year.
Duration of study	
Twenty four months:
 
Month 1-8: (1) Analyze existing practice patterns focused on 6 decision nodes derived from the NCCN decision tree for NSCLC. The study of practice patterns will be based on primarily on review of medical records by a trained research coordinator under [name] direction. (2) Programming of NSCLC decision aid under [name] direction, conducted with technical assistance as needed from PwP. The results will be reviewed by co-investigators for accuracy and ease of use.
 
Month 8-20: Conduct prospective trial of the decision aid, collecting data directly from patients over the course of their initial 2 consultations.
 
Month 20-24: Completion of data collection and data analysis activities.

Study Intervention	The interactive PwP interface allows structured exploration of choices, sequencing, and timing of therapies. The aid thus enables the patient to discuss proposed treatments with the oncologist (rather than assuming passive acceptance). Furthermore, the decision aid allows evolving display of the treatment choices and timeline/calendar in a graphical, simplified format during the discussion (rather than assuming absorption and recall of details of a verbal communication). We will collect pilot data related to the collaborative, patient-oriented approach facilitated by this decision aid.
Study Assessments	
A total of five patient-reported instruments will be used to score overall and lung cancer-specific quality of life, decision-support preferences, decisional conflict, and satisfaction with decision:
 
 1. Decision Support Preference Questionnaire (DMPQ) 2. FACT-L 3. FACT/NCCN-Lung Symptom Index (NCCN-FACT FLSI-17) 4. Decisional Conflict Scale (DCS) 5. Post-Consultation Questionnaire 6. Satisfaction with Health Care Decision (SWD)

1.1 Background on Intervention

Many physicians are reluctant to disclose specific details to cancer patients, such as risks of treatment, prognosis and treatment alternatives.¹⁻⁴ Communication is complicated by the stigma and fear associated with cancer,⁵ the complexity of the information, and uncertainty about the course of the disease and benefits of treatment.^{6,7} Discussions of treatment options are detailed and prolonged, leading to information loss and misunderstandings. However, the literature shows that providing detailed information to patients has not been associated with adverse psychological sequelae and, in some studies, it has contributed to decreased anxiety and increased treatment adherence.

Most educational interventions for cancer patients aim to help manage side effects, decrease anxiety, and increase compliance.⁸⁻¹³ Recently, decision aids have been developed, to help patients go beyond traditional educational interventions by engaging them more directly in the decision process.¹⁴ Major types of decision aids are interactive videos, personalized audiotapes, or booklets. In its systematic review, the Cochrane Collaboration found that these interventions improved knowledge and encouraged more appropriate use of surgical interventions.¹⁵

A few studies have explored decision aids used jointly and interactively by physicians and patients during a consultation. Whelan et al. found that a Decision Board intervention for breast cancer patients was associated with increased knowledge and use of breast-conserving surgery.¹⁶⁻¹⁸ Siminoff et al. tested Adjuvant Online with early-stage breast cancer patients and found that the intervention group was more knowledgeable and less likely to choose adjuvant therapy featuring very marginal benefit.¹⁹⁻²¹

This study will test an innovative, interactive decision aid designed to facilitate patient and oncologist decision-support as a team. Improved patient-physician communication is likely to yield benefits in knowledge, decision certainty, and satisfaction.

1.2 Patients with Power – An Innovative Decision Aid to Visualize NCCN Guidelines

The decision aid in this study will be developed in collaboration with a technology startup, Patients with Power (PwP). PwP has developed an innovative web-based software that displays content excerpted from the NCCN patient guidelines. The interactive web interface allows physicians or patients to input an individual patient's characteristics and then, drawing from the NCCN-guidelines-based decision trees, to design a patient-specific decision tree accompanied by a timeline tying anticipated procedures to specific dates. At present, PwP has developed a proof of concept only for breast cancer, but PwP has shared proprietary data with the Principal Investigator establishing the feasibility of customizing the interface for NSCLC-related content.

The interactive PwP interface allows structured exploration of choices, sequencing, and timing of therapies. The aid thus enables the patient to discuss proposed treatments with the oncologist (rather than assuming passive acceptance). Furthermore, the decision aid allows evolving display of the treatment choices and timeline/calendar in a graphical, simplified format during the discussion (rather than assuming absorption and recall of details of a verbal communication). We will collect pilot data related to the collaborative, patient-oriented approach facilitated by this decision aid.

1.2.1 Patients' Reactions to PwP Proof of Concept

The PwP prototype decision aid has met with very positive responses in the breast cancer community:

From a newly diagnosed patient: “[I]t is amazing. It seems that my surgeon is following the right course. She has not talked about chemotherapy yet since the surgery comes first and then pathology.... My surgeon is also interested in learning more about this software.”

From a 2-year survivor: “[K]nowing the NCCN guidelines as compared to what doctors are recommending is really valuable.”

[figure not shown]
From a 6-year survivor: “I love the concept and the sleek, clean, bright design.... With your drop down lists, it was a snap to pick the correct answers. Your site has the potential to be a great source of information for hungry patients. I would have loved to have had something like it when I went through treatment.”

From a friend of a patient: “She and I went on[line] together. She is not tech savvy so I wasn't sure how she would react. I am a geek so it makes perfect sense to me. She really liked it and was able to navigate around with ease.... We especially liked the fact that information was available at decision points where choices would need to be made. That makes the journey a whole lot less confusing.”

From a cancer survivor and activist: “If this existed when I'd been diagnosed, it would've been the compass to help guide and map out my journey.”

Startup technology companies often launch prototypes in high-profile diseases such as breast cancer. This project will extend the innovation to a more marginalized and underserved population in NSCLC. While extending the concept to NSCLC, our project will preserve the core features of the decision aid, including the graphical visualization of the guidelines, the ease of navigation in the user interface, the personalization enabled by the drop-down boxes, and the ability to create, modify, and review multiple scenarios (see Figure 1).

Figure 1. Screenshot of Patients with Power decision aid, designed currently for patients with breast cancer.

1.3 Rationale for the Proposed Study

This is a two-year career development project to develop and field-test a decision aid based on the NCCN patient guidelines for NSCLC. The study goal is to improve the treatment decision-support process in NSCLC patients in an academic medical center. If successful, this decision aid will be disseminated more broadly to community settings.

This study will consist of a development phase followed by an evaluation phase. After initial prototyping, refinement, coding, and implementation of the intervention, a study will be implemented using a pre/post design to estimate the effect size of the intervention with respect to disseminating NCCN-guided treatment choices (primary outcome) and to generate preliminary data about secondary outcomes.

Specifically, this project will:

1. Characterize physician and patient populations and treatment decisions in the UCSF thoracic oncology practices.
2. Establish the acceptability, feasibility, and effectiveness of a novel decision aid for decisions made about treatment for NSCLC.

3. Conduct an evaluation of changes in NCCN-guided practice patterns before and after implementation of the decision aid, with respect to 6 clinical scenarios:

1. All patients: if smoking cessation intervention is provided at initial visit;
2. Stage IB-IIB patients receiving surgery: if adjuvant chemotherapy is given after surgery;
3. Stage III patients receiving surgery: if pathologic staging of mediastinal nodal disease is done prior to initiation of therapies;
4. Stage III patients not receiving surgery: if pathologic staging of mediastinal nodal disease is done prior to initiation of therapies
5. Stage III patients not receiving surgery: if concurrent chemoradiation is given upfront;
6. Stage IV patients: if molecular testing is done prior to initiation of systemic therapy.

4. Collect data to facilitate the design of future larger-scale evaluations, including assessments of physician-patient agreement and patients' levels of decisional conflict and satisfaction with decisions made.

2 Objectives of the Study

2.1 Primary

The primary study outcomes will emerge from measurement of changes in overall practice patterns after implementation of the decision aid. Pre- and post-intervention data will be used to determine the level of difference before and after implementation of the decision aid into the thoracic oncology clinics. Six specific practice patterns will be queried in a binary (yes/no) manner:

1. All stages: smoking cessation discussion reinforced with a specific followup plan and/or medication/patch/psychotherapy or counseling;
2. Stage IB, IIA, IIB receiving surgery: adjuvant chemotherapy given after surgery;
3. Stage III receiving surgery: pathologic staging of mediastinal nodal disease prior to initiation of therapies;
4. Stage III not receiving surgery: pathologic staging of mediastinal nodal disease prior to initiation of therapies
5. Stage III patients not receiving surgery: if concurrent chemoradiation is given upfront
6. Stage IV: molecular testing for EGFR and ALK mutations prior to initiation of systemic therapy.

2.2 Secondary

Secondary objectives are to:

1. Determine agreement between patient and physician post-consultation reports of treatments discussed and recommended, prognosis, and expected tolerance.

2. Determine correlations between overall and lung cancer-specific quality of life and decision-support preferences.
3. Determine correlations between overall and lung cancer-specific quality of life and decisional conflict.
4. Determine correlations between overall and lung cancer-specific quality of life and satisfaction with decision.
5. Determine correlations between decision-support preferences and decisional conflict and satisfaction with decision.
6. Determine correlations between decisional conflict and satisfaction with decision.

2.3 Endpoints

2.3.1 Primary Endpoints

The practice pattern survey completed during the first 8 months will provide the baseline data that will be compared to results obtained after implementation of the decision aid.

2.3.2 Secondary Endpoints

A total of five patient-reported instruments will be used to score overall and lung cancer-specific quality of life, decision-support preferences, decisional conflict, and satisfaction with decision:

1. Decision Support Preference Questionnaire (DMPQ)
2. FACT-L
3. ACT/NCCN-Lung Symptom Index (NCCN-FACT FLSI-17)
4. Decisional Conflict Scale (DCS)
5. Post-Consultation Questionnaire
6. Satisfaction with Health Care Decision (SWD).

3 Study Design

3.1 Number of Subjects

The total number of participants to be enrolled is 250. The expected number of participants to be enrolled per quarter is 60-65.

3.2 Eligibility Criteria

The patient must be thoroughly informed about all aspects of the study, including the study visit schedule and required evaluations and all regulatory requirements for informed consent. The written informed consent must be obtained from the patient prior to enrollment. The following criteria apply to all patients enrolled onto the study unless otherwise specified.

3.2.1 Inclusion Criteria

1. Over age of 18

2. Able to provide informed consent
3. Able to use a web-based interface
4. Histologically proven or clinically apparent diagnosis of non-small cell lung cancer. Eligible NSCLC histological types include:
 - Adenocarcinoma
 - Squamous Cell Carcinoma
 - Large Cell Carcinoma
 - Adenosquamous Carcinoma
5. Newly diagnosed, with new primary occurrence of NSCLC, or diagnosed with a new recurrence or new progression of existing disease, and not yet treated for the new problem.
6. Being seen in consultation at the UCSF thoracic oncology clinics

3.2.2 Exclusion Criteria

1. Unable to fill out questionnaires
2. Already treated for the current diagnosis of a new primary occurrence of NSCLC, or already treated for the new recurrence or new progression of existing disease.

3.3 Duration of Intervention

The patients will have access to the decision support tool indefinitely (lifetime) but collection of all study metrics will end at 12 months after the period of their first 2 initial consultations for NSCLC.

3.4 Duration of Follow Up

Questionnaires will be completed at the time of initial consultation, with no planned follow up; PwP website-based metrics will be followed in aggregate for a maximum of 1 year.

3.5 Study Timeline

Month 1-8:

(1) Analyze existing practice patterns focused on 6 decision points derived from the NCCN decision tree for NSCLC (see Main Scientific Question). The study of practice patterns will be based on direct observation of new patient visits coded by a trained research coordinator and review of medical records.

(2) Programming of NSCLC decision aid by a research fellow under my direction, conducted with technical assistance as needed from PwP. The results will be reviewed by co-investigators for accuracy and ease of use.

Month 8-20: Conduct prospective trial of the decision aid.

Month 21-27: Completion of data collection and data analysis activities.

First Participant in (estimated date of first participant enrolled): from 6/1/2014 to 2/23/2015

Last Participant in (estimated date of last participant enrolled): from 5/31/2015 to 8/1/2015

Last Participant Last Visit (estimated date of completion of Therapy for all participants enrolled): from 5/31/2015 to 8/1/2015

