6.1 Study Endpoints

Primary Endpoints: The practice pattern survey completed during the first 8 months will provide the baseline data that will be compared to results obtained after implementation of the decision aid.

Secondary Endpoints: A total of five patient-reported instruments will be used to score overall and lung cancer-specific quality of life, decision-support preferences, decisional conflict, and satisfaction with decision:

Decision Support Preference Questionnaire (DMPQ)

FACT-L

FACT/NCCN-Lung Symptom Index (NCCN-FACT FLSI-17)

Decisional Conflict Scale (DCS)

Post-Consultation Questionnaire

Satisfaction with Health Care Decision (SWD).

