6.1.1 Study Design

This study involves the evaluation of the decision support tool Patients with Power, previously used with breast cancer patients, in the non-small cell lung cancer patient population.

1. Characterize physician and patient populations and treatment decisions in the UCSF thoracic oncology practices.
2. Establish the acceptability, feasibility, and effectiveness of a novel decision aid for decisions made about treatment for NSCLC.
3. Conduct an evaluation of changes in NCCN-guided practice patterns before and after implementation of the decision aid, with respect to 6 clinical scenarios:

All patients: if smoking cessation intervention is provided at initial visit;

Stage IB-IIB patients receiving surgery: if adjuvant chemotherapy is given after surgery;

Stage III patients receiving surgery: if pathologic staging of mediastinal nodal disease is done prior to initiation of therapies;

Stage III patients not receiving surgery: if pathologic staging of mediastinal nodal disease is done prior to initiation of therapies;

Stage III patients not receiving surgery: if concurrent chemoradiation is given upfront;

Stage IV patients: if molecular testing is done prior to initiation of systemic therapy.

4. Collect data to facilitate the design of future larger-scale evaluations, including assessments of physician-patient agreement and patients' levels of decisional conflict and satisfaction with decisions made as well as potential correlations to patient-reported quality to life.

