6.2 Determination of Sample Size and Accrual Rate

6.2.1 Sample Size and Power Estimate

We expect that the clinical volume of 30 patients/month for 12 months will yield a potential enrollment pool of 360 patients. Anticipating a 30% decline, dropout, or ineligibility rate at the time of potential enrollment, then at least 250 patients should be evaluable. The sample size was determined based on the primary outcomes of changes in practice patterns. For each disease stage, a test of at least a 25% improvement using the decision aid compared with the pre-intervention results in the proportion of patients satisfying the stage-specific criterion listed above will be carried out (see Primary Endpoint for practice pattern metrics). In addition, the entire study sample will be evaluated to test for a change in smoking cessation plans. Patients will be included in up to 3 individual analyses. The maximum sample size for any one test is based upon assuming a null hypothesis of 50% in the pre-intervention cohort. This estimate for the null hypothesis will be modified using the results obtained prior to use of the decision aid (Months 1-8). Based upon the one-sample binary exact test with power set at 90% and a 2-sided type I error of 0.017 (adjusted for up to 3 tests for all patients), 53 patients would be required for each test. The test would reflect the actual accrual by stage with the use of the decision aid. With a fixed type I error of 0.017, this means for any individual test that the sample size may differ from 53, and the null hypothesis may differ from 50% and result in reduced power but will be at least 80%. For example, if adjuvant chemotherapy is given after surgery to 40% of stage IB and II patients determined from the pre-intervention assessment, then a test to detect a 50% improvement to 60% will require 70 patients with 80% power and 88 patients with 91% power. Similarly, if 60% of patients satisfy the smoking cessation criterion during the

pre-intervention interval, a 50% improvement will require 32 patients with 92% power, but a 15% improvement with 90% power requires 135 patients across all disease stages. It is therefore not anticipated that the comparisons will require more than the expected enrollment of 250 patients.

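### The six practice patterns are not measured alike before and after the aid, so the primary one-sample test can shift with no effect of the aid, most clearly for adjuvant chemotherapy

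*Combined protocol and SAP*

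**What the plan says.** Section 1.3 gives the study's purpose as a pre/post design "to estimate the effect size of the intervention with respect to disseminating NCCN-guided treatment choices (primary outcome"). Section 6.1 states: "The practice pattern survey completed during the first 8 months will provide the baseline data that will be compared to results obtained after implementation". Section 6.2.1 plans a one-sample exact test with an assumed null of 50% and adds: "This estimate for the null hypothesis will be modified using the results obtained prior to use of the decision aid (Months 1-8").

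**Window.** The second practice pattern in section 2.1 (metric 2) is "Stage IB, IIA, IIB receiving surgery: adjuvant chemotherapy given after surgery". No per-patient window is given for it in either period. After the aid, section 3.3 ends metric collection 12 months after the first two consultations. The abstract places completion of data collection and analysis in months 20-24, section 3.5 in months 21-27, and section 3.5.1 within 4 months of accrual closing.

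**Source.** For the baseline, section 3.5 says that "practice patterns will be based on direct observation of new patient visits coded by a trained research coordinator and review of medical records", whereas the abstract says mainly record review. For the post-aid period the abstract speaks of collecting data directly from patients over two consultations. Section 5.1 adds a Post-Consultation Questionnaire on treatments discussed, recommended and chosen. Neither is tied to the six metrics.

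**Population.** Section 3.2 applies to enrolled patients. They must consent, be able to use a web interface and fill out questionnaires, and be untreated for the current problem. Section 6.2.1 allows for losses: "Anticipating a 30% decline, dropout, or ineligibility rate at the time of potential enrollment". For the baseline, NSCLC and the clinic setting are implied by sections 3.5 and 6.1.1, but the not-yet-treated criterion is not stated.

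**The concern.** There is no concurrent control. Any difference in how the two rates are measured therefore enters both the effect estimate and the test as if it were an effect of the aid.

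Metric 2 is the most exposed. Enrolled patients are untreated at consultation, so surgery and then chemotherapy come later. A baseline closed at month 8 misses late events that a longer post-aid follow-up would catch. The surgery/no-surgery split that defines metrics 3-5, and upfront chemoradiation in metric 5, also need some follow-up, but to a lesser degree.

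Source matters mainly for metric 1 (smoking cessation), where an observer may record a discussion that the chart omits. Selection matters because only the post-aid group is filtered by consent, web ability and questionnaires.

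**Working it through.** **1. The plan's own figure.** Inputs from 6.2.1: exact binomial test, two-sided 0.017 (0.0085 per tail), null 50%, n=53. Reading the 25% improvement as 50% to 75%, the test rejects at 36 or more, or 17 or fewer. Actual size is 0.0127 and power 0.908, so the stated 53 patients at 90% power reproduces.

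**2. Post-aid timelines.** Accrual runs over months 8-20. A patient enrolled at month 20 would reach the 12-month limit at 20 + 12 = month 32. The abstract stops at month 24, section 3.5.1 at 20 + 4 = month 24, and section 3.5 at month 27, and all three include analysis time.

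**3. Metric 2 with the baseline closed at month 8.** The documents give no lags, so these are assumed. First visits are uniform over months 0-8, surgery comes s months and chemotherapy d months after consultation, and the true rate is 50% in both periods. The denominator is patients operated on by month 8, those without chemotherapy by then are scored no, and the baseline rate is treated as known.

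Captured share = (8 − d)/(8 − s); baseline rate = 0.50 × share. For d ≤ 4, post-aid capture is complete by month 24 (20 + 4), so the post-aid rate is 0.50.

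| s, d | Share | Baseline rate | Rejects, n=53 | Rejects, n=30 |
|---|---|---|---|---|
| 1, 2 | 6/7 = 0.857 | 0.429 | 8.5% | 5.0% |
| 2, 3 | 5/6 = 0.833 | 0.417 | 8.5% | 5.0% |
| 3, 4 | 4/5 = 0.800 | 0.400 | 13.6% | 10.0% |
| 1, 3 | 5/7 = 0.714 | 0.357 | 39.2% | 18.1% |
| 2, 4 | 4/6 = 0.667 | 0.333 | 50.0% | 29.2% |
| Aligned | 1 | 0.500 | 1.3% | 1.6% |

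In the first five rows nearly all rejections are in the direction of improvement. The false gain is 7-10 points for a 1-month lag from surgery and 14-17 points for 2 months, against the 25 points the test is sized for.

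**4. The opposite sign.** Suppose the baseline is complete, d = 6 and the post-aid cutoff is month 24. The post-aid share is (24 − 8 − 6)/(24 − 8 − s) = 10/(16 − s). For s = 5 the post-aid rate is 0.455 and the test rejects 3.4% of the time at n=53. For s = 4 it is 0.417 and 10.0%. Nearly all of these rejections are downward.

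**5. Selection, metric 1.** Assume a clinic-wide rate of 60%, n=250, a share f of the pool with no counterpart filter at baseline, and a rate q in the non-enrolled. Enrolled rate = (0.60 − f·q)/(1 − f). With no selection the test rejects 1.4% of the time.

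| f | q = 0.50 to 0.45 (upward) | q = 0.70 to 0.75 (downward) |
|---|---|---|
| 0.10 | 2.2-3.1% | 1.9-2.7% |
| 0.20 | 5.4-11.5% | 4.6-9.9% |
| 0.30 | 15.2-37.5% | 13.2-33.2% |

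**6. A separate component.** Steps 3-5 treat the baseline rate as known, but 6.2.1 sets the null from observed results. Averaging the test's rejection rate over the binomial distribution of the baseline count, with identical measurement in both periods, gives 7.0% for 53 v 53 patients at 50% and 8.9% for 240 v 250 at 60%. The nominal level is 1.7%. (The 240 assumes 30 patients a month for 8 months.)

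**The case against.** The strongest reply is that the gap is narrow and the large figures rest on stacked assumptions. Most of this stands:

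- **Anchors.** A reader might infer that all six metrics lack a window. They do not. Staging is tied to the start of treatment, as in "Stage III not receiving surgery: pathologic staging of mediastinal nodal disease prior to initiation of therapies", and so is molecular testing. Section 6.1.1 places metric 1 at the first visit: "All patients: if smoking cessation intervention is provided at initial visit".
- **Baseline eligibility.** A reader might infer that baseline patients could be anyone. Disease and setting are implied. What is missing is the explicit histology and prior-treatment criteria.
- **Source.** The plan is not silent on post-aid collection, as the abstract and section 5.1 show. The gap is that neither description is linked to the six metrics.
- **Older charts.** The abstract describes existing practice studied mainly from records. That would permit older, fully followed charts, and step 3 would then vanish. The plan allows this but does not require it. Observation of new visits in months 1-8 points the other way.
- **Regression.** The logistic regression in 6.3.1 may reduce case-mix differences if the same covariates are collected at baseline. It cannot recover events outside a window or missed by a source.

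A pilot pre/post design is legitimate. It still needs numerator, denominator and window defined alike in both periods.

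**Conclusion.** The concern holds in limited form. No section gives a common window, source or set of criteria for the two rates that the primary test compares. The clearest exposure is metric 2. On the stated assumptions (visits limited to months 1-8, closure at month 8, incomplete patients scored no, known baseline rate), the false-rejection risk at n=53 is 8-14% or 39-50%, depending on the lag.

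Two stronger readings are not supported. One is that the study will show a spurious gain: a short post-aid cutoff pushes downward, selection can act either way, and the net direction is unknown. The other is that aligning the windows restores the nominal error rate. The 1.3% figure applies only to a known baseline, and the inflation in step 6 would remain.

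This should be corrected. Confidence is medium, because the lags and rates are assumed.

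**What to change.** 1. Score all six metrics in both periods from the medical record with one abstraction form. Where direct observation is used for metric 1, use it in both periods or report it only as supplementary.
2. For metric 2, use one fixed measurement window W from surgery in both periods. Count only patients whose full window falls before that period's data cutoff, and do not score incomplete windows as no. For metrics 3-5, assess surgery status at one fixed time from first consultation in both periods.
3. Apply the histology and not-yet-treated criteria (3.2.1 items 4-5 and exclusion 2) to baseline charts.
4. Reconcile the abstract with sections 3.3, 3.5 and 3.5.1.
5. Report consent, web and questionnaire selection, and calendar-time trends, as limitations.

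None of this removes the inflation from treating an estimated baseline as fixed, which needs its own remedy.

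**Cost.** Protocol wording, one form and fewer evaluable metric 2 patients. As an illustration, assume W = 3 months, surgery 1-3 months after consultation, 2 months kept for analysis and uniform 12-month accrual. The evaluable post-aid share is (cutoff − W − s − 8)/12, capped at 1. That is 67-83% with cutoff at month 22 (24 − 2) and 92-100% at month 25 (27 − 2). Baseline charts limited to months 1-8 would give (8 − 3 − s)/8 = 25-50%, so older charts may be needed. These widen the calendar gap between cohorts. The shares depend on the accrual period, and the later enrolment dates in section 3.5 (2/23/2015 to 8/1/2015) may imply only about 5 months.
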